6.4 Subject Disposition

Subject disposition will be summarized as follows:

- The number of subjects in each analysis set will be summarized by study part, period (where applicable), treatment group and overall for all enrolled subjects.
- The number of early withdrawals and the reasons for withdrawals will be tabulated by study part, period (where applicable), treatment group and overall for all enrolled subjects.

6.5 Protocol Deviations

A listing of protocol deviations will be provided within Appendix 16.2.

6.6 Baseline Comparability

The comparability of treatment groups with respect to subject demographics and baseline characteristics will be assessed in a descriptive manner, but no formal statistical testing will be performed. The Safety Analysis Set will be used to summarize all baseline and demographic data.

6.7 Demographic Data

Standard continuous or categorical variable summaries will be presented by treatment group for the following variables based on the Safety Analysis Set.

QMD Ref: Worldwide-TMP-ST-006-4.0 Effective: 12Aug2019	Governing QMD: Worldwide-SOP-ST-001
Confidentiality Statement	

This document is the property of Worldwide Clinical Trials Inc. and may not be duplicated, copied, altered or removed from company without prior approval from Worldwide Quality Assurance or in compliance with Worldwide Standard Operating Procedures.

Worldwide Clinical Trials Controlled Quality Management Document			
 WORLDWIDE CLINICAL TRIALS	Sponsor:	TB Alliance	
Protocol Number:			TBI-223-CL-001

STATISTICAL ANALYSIS PLAN – PHASE 1

- Age at Informed Consent (years)
- Sex
- Ethnicity
- Race, where more than one race is selected the subject will be presented under the ‘Multiple races’ category in the summary but each selected race will be identified in the listing.
- Weight at Screening (kg)
- Height at Screening (cm)
- BMI at Screening (kg/m²)

6.8 Medical History

Separate listings of previous and ongoing conditions at Screening will be presented for the Safety Set. Conditions will be coded using the Medical Dictionary of Regulated Activities (MedDRA version 21.0 or higher) primary system organ class (SOC) and preferred term (PT). Any medical condition will be classed as resolved if a stop date is recorded, otherwise, the condition will be classed as ongoing.

6.9 Prior and Concomitant Medications

Prior and concomitant medications will be listed for the Safety Analysis Set. Prior medications are defined as all medications starting and stopping before the date of first dose of study drug. Concomitant medications are defined as medications taken on or after the date of first dose of study drug. Each concomitant medication will be assigned to the last study drug taken prior to starting the concomitant medication. Prior and concomitant medications will be coded using the World Health Organization (WHO) Drug Dictionary B3 – September 2018 version.

6.10 Exposure to Study Drug

All dosing information will be listed.

6.11 Pharmacokinetic Analyses

Concentration-time data will be tabulated by nominal time, analyte, and cohort using descriptive statistics. For presentation of the individual data and summary statistics, concentrations below the limit of quantitation (BLQ) will be set to zero.

Mean and individual subject concentration-time data will be presented graphically on linear and semi-logarithmic scales. Mean concentration-time data will be presented for all doses and for fed vs. fasted cohorts. Mean data will be plotted using nominal sample times, and individual data will

QMD Ref: Worldwide-TMP-ST-006-4.0 Effective: 12Aug2019	Governing QMD: Worldwide-SOP-ST-001
Confidentiality Statement	

This document is the property of Worldwide Clinical Trials Inc. and may not be duplicated, copied, altered or removed from company without prior approval from Worldwide Quality Assurance or in compliance with Worldwide Standard Operating Procedures.

Worldwide Clinical Trials Controlled Quality Management Document			
 WORLDWIDE CLINICAL TRIALS	Sponsor:	TB Alliance	
Protocol Number:			TBI-223-CL-001
STATISTICAL ANALYSIS PLAN – PHASE 1			

be plotted using actual times. For all subject plots (spaghetti plots, all subjects per treatment in one plot), subjects will be identified by subject number in the legend.

PK parameters will be calculated as described in Section 6.2.9.

PK parameters will be summarized by analyte and cohort using descriptive statistics.

Part 1; Dose Proportionality (Cohorts 1-7, fasted conditions):

The pharmacokinetic parameters C_{max} , AUC_{last} , and AUC_{inf} for TBI-223 for fasted cohorts will be compared across doses to assess dose proportionality (i.e., proportionality of a change in systemic exposure with a change in dose). Statistical analyses will be done using a power model (Smith, 2000) of the following general form,

$$\ln(\text{PK}) = \ln(\beta_0) + \beta_1 \cdot \ln(\text{Dose}) + \varepsilon,$$

where

PK is the pharmacokinetic parameter tested (e.g. C_{max} or AUC)

$\ln(\beta_0)$ is the y-intercept,

β_1 is the slope (a value of $\beta_1 \approx 1$ indicates linearity), and

ε is an error term

The estimate of β_1 with the 90% CIs will be reported along with the dose range for proportionality.

Part 1; Food Effect (Cohort 5):

Statistical comparison of the PK parameters of exposure (C_{max} , AUC_{last} , and AUC_{inf}) will be performed using an Analysis of Variance (ANOVA) model for a 2-way crossover design on the ln-transformed data with treatment as the fixed effects and subject as a random effect. Conclusions regarding the results of the statistical analysis of PK parameters across treatments will be based on the ratio of the geometric means expressed as a percent (100×Fed/Fasted) and the 90% confidence interval about the ratio. A lack of food effect will be demonstrated if the 90% confidence intervals are fully contained within the limits of 80.00% to 125.00%.

QMD Ref: Worldwide-TMP-ST-006-4.0 Effective: 12Aug2019	Governing QMD: Worldwide-SOP-ST-001
Confidentiality Statement	
This document is the property of Worldwide Clinical Trials Inc. and may not be duplicated, copied, altered or removed from company without prior approval from Worldwide Quality Assurance or in compliance with Worldwide Standard Operating Procedures.	

Worldwide Clinical Trials Controlled Quality Management Document			
 WORLDWIDE CLINICAL TRIALS	Sponsor:	TB Alliance	
	Protocol Number:	TBI-223-CL-001	
STATISTICAL ANALYSIS PLAN – PHASE 1			

Part 1; Cohort 3 Repeat:

Statistical comparison of the PK parameters of exposure (C_{max} , AUC_{last} , and AUC_{inf}) will be performed using an Analysis of Variance (ANOVA) model for a two-way crossover design on the ln-transformed data with treatment as a fixed effect and subject as a random effect. Conclusions regarding the results of the statistical analysis of PK parameters across treatments will be based on the ratio of the geometric means expressed as a percent (100 \times Test/Reference; TBI-223 oral enteric capsules, Cohort 3 repeat vs. TBI-223 oral suspension, Cohort 3) and the 90% confidence interval about the ratio. Similar bioavailability will be demonstrated if the 90% confidence intervals are fully contained within the limits of 80.00% to 125.00%.

Part 2; Cohorts 8 and 9:

Statistical comparison of the PK parameters of exposure (C_{max} , AUC_{last} , and AUC_{inf}) will be performed using an Analysis of Variance (ANOVA) model for a parallel design on the ln-transformed data with treatment as a fixed effect. Conclusions regarding the results of the statistical analysis of PK parameters across treatments will be based on the ratio of the geometric means expressed as a percent (100 \times Test/Reference) and the 90% confidence interval about the ratio. The following comparisons will be made:

- IR, 2000 mg (2 x 1000 mg tablets) / FED (Cohort 9) vs. IR, 2000 mg (2 x 1000 mg tablets) / FASTED (Cohort 8)
- SR (Prototype 1, 2 or 3), 1800 mg (2 x 900 mg tablets) / FED (Cohort 8) vs. , 2000 mg (2 x 1000 mg tablets) / FASTED (Cohort 8)
- SR (Prototype 1, 2 or 3), 1800 mg (2 x 900 mg tablets) / FED (Cohort 8) vs. IR, 2000 mg (2 x 1000 mg tablets) / FED

Note: 1800 mg TBI-223 SR Tablets will be dose-normalized to 2000 mg for the purpose of statistical comparisons.

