## Part 2:

Cohort 8: A minimum of 24 subjects in 4 dosing arms are planned to be enrolled; within each arm, 6 subjects will be assigned to receive a single dose treatment. Subjects will be assigned to one of the following arms and dose:

- Arm 1 – TBI-223 SR Tablets (Prototype 1) - 1800 mg dose (3 x 600 mg tablets), under fed conditions
- Arm 2 – TBI-223 SR Tablets (Prototype 2) - 1800 mg dose (3 x 600 mg tablets), under fed conditions
- Arm 3 – TBI-223 SR Tablets (Prototype 3) - 1800 mg dose (2 x 900 mg tablets), under fed conditions
- Arm 4 – TBI-223 IR Tablets - 2000 mg dose (2 x 1000 mg tablets), under fasting conditions

Procedures and analyses will be conducted as outlined in Appendix 6.

Cohort 9: The 6 subjects from Cohort 8, Arm 4, who received the IR tablet formulation fasted will return after a 7-day washout and receive a single dose of TBI-223 IR Tablets, 2000 mg dose (2 x 1000 mg tablets), under fed conditions.

If more than 2 subjects of these 6 subjects from Cohort 8 drop-out, they will be replaced by healthy volunteers (a minimum of 4 subjects are needed to complete Cohort 9).

Procedures and analyses will be conducted as outlined in Appendix 6.

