#### **6.4 Confinement**

Part 1 fasting cohorts, and Part 2, Cohort 8, Arm 4 only: Subjects will be admitted to the research center on Day -2 (Part 1) or Day -1 (Part 2) and remain confined until after completion of the 48-hour procedures on Day 3. Subjects will return for a follow-up visit approximately 72 hours after dosing (Day 4) and receive a follow up phone call on Day 11 (+1 day).

Part 1 food-effect cohort, Part 2, Cohort 8, Arms 1-3 and Cohort 9: Subjects will be admitted to the research center on Day -2 of Period 1 and Period 2 (Part 1) or Day -1 (Part 2) and remain confined until after completion of the 48-hour procedures on Day 3 of each study period. Subjects will return for a follow-up visit approximately 72 hours after dosing (Day 4) in each study period. Subjects will receive a follow up phone call on Day 11 (+1 day) of Period 2.

Please note that Cohort 9 is the same 6 subjects that were in Cohort 8, Arm 4 (IR tablet formulation) under fed conditions. In Cohort 8, Arm 4, subjects fasted.

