1 INTRODUCTION

This document details the planned statistical analyses for the Global Alliance for TB Drug Development, protocol “TBI-223-CL-001” study titled “A Phase 1, Partially-Blinded, Placebo-Controlled, Randomized Single Ascending Dose (SAD) with a Food Effect Cohort Study to Evaluate the Safety, Tolerability, and Pharmacokinetics of TBI-223 in Healthy Adult Participants”. The proposed analyses are based on the contents of protocol version 3.0, dated 21-Jan-2020 and Protocol Clarification Letter No. 4, dated 24-Feb-2020.

This is a partially blinded, placebo-controlled, randomized, SAD study with a food effect cohort. The study will be conducted at one study center in the United States.

Part 1

Part 1 of the study will have up to 6 planned dose levels. Based on interim pharmacokinetic data obtained during the dose escalation, a dose cohort will be selected to return for additional dosing after a high-calorie, high-fat meal (food-effect cohort).

Part 2

Part 2 of the study will comprise 4 arms each consisting of 6 subjects. Subjects will be assigned to one of the following dosing arms:

Arm 1	TBI-223 SR Tablets (Prototype 1) - 1800 mg dose (3 x 600 mg tablets) under fed conditions
Arm 2	TBI-223 SR Tablets (Prototype 2) - 1800 mg dose (3 x 600 mg tablets) under fed conditions
Arm 3	TBI-223 SR Tablets (Prototype 3) - 1800 mg dose (2 x 900 mg tablets) under fed conditions
Arm 4	TBI-223 IR Tablets - 2000 mg dose (2 x 1000 mg tablets) under fasting conditions

*IR = Immediate Release; SR = Sustained Release

The 6 subjects from Arm 4, who received the IR tablet formulation will be brought back following a 7-day washout period to receive TBI-223 IR Tablets 2000 mg (2 x 1000 mg tablets), under fed conditions. If more than 2 of the 6 subjects drop-out, they will be replaced by healthy volunteers (a minimum of 4 subjects is required to complete the Fed cohort).

Additional cohorts may be enrolled if deemed appropriate (e.g. if bioavailability is lower than expected) by the Sponsor to repeat a dose level, to study other dose levels, change proposed

QMD Ref: Worldwide-TMP-ST-006-4.0 Effective: 12Aug2019	Governing QMD: Worldwide-SOP-ST-001
Confidentiality Statement	

This document is the property of Worldwide Clinical Trials Inc. and may not be duplicated, copied, altered or removed from company without prior approval from Worldwide Quality Assurance or in compliance with Worldwide Standard Operating Procedures.

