16.2.2	Protocol Deviations		
16.2.2.1	Protocol Deviations – Safety Analysis Set	IP	
16.2.3	Subjects Excluded from The Efficacy Analyses		
16.2.3.1	Analysis Sets - All Enrolled Subjects	IP	
16.2.4	Demographic Data		
16.2.4.1	Demographic Data – Safety Analysis Set	IP	
16.2.4.2	Previous and Ongoing Medical History – Safety Analysis Set	IP	
16.2.5	Compliance and/or Drug Concentration Data		
16.2.5.1	PK Sampling Data – Safety Analysis Set	IP	
16.2.5.2	Dosing Information – Safety Analysis Set	IP	
16.2.5.3	Prior and Concomitant Medication – Safety Analysis Set	IP	
16.2.6	Individual Efficacy Response Data		
16.2.6.1	Plasma TBI-223 and TBI-223 M2 Concentration Listing by Subject (Part 1)	MR	
16.2.6.2	Plasma TBI-223 and TBI-223 M2 Concentration Listing by Subject (Part 2)		
16.2.6.3	Terminal Elimination Rate of TBI-223 and TBI-223 M2 in Plasma for Individual Subjects (Part 1)	MR	
16.2.6.4	Terminal Elimination Rate of TBI-223 and TBI-223 M2 in Plasma for Individual Subjects (Part 2)		
16.2.6.5	PK Output for TBI-223 and TBI-223 M2	MR	
16.2.6.6	Statistical Analysis SAS Output for Dose Proportionality (Part 1)	MR	
16.2.6.7	Statistical Analysis SAS Output for Food Effect Assessment (Part 1, Cohort 5)	MR	
16.2.6.8	Statistical Analysis SAS Output for Formulation Effect Assessment (Part 1, Cohort 3 and Cohort 3 Repeat)	MR	
16.2.6.9	Statistical Analysis SAS Output for Food Effect Assessment (IR tablets; Part 2)	MR	
16.2.6.10	Statistical Analysis SAS Output (SR Fed vs. IR Fasted; Part 2)	MR	

QMD Ref: Worldwide-TMP-ST-006-4.0 Effective: 12Aug2019	Governing QMD: Worldwide-SOP-ST-001
Confidentiality Statement	
This document is the property of Worldwide Clinical Trials Inc. and may not be duplicated, copied, altered or removed from company without prior approval from Worldwide Quality Assurance or in compliance with Worldwide Standard Operating Procedures.	

Worldwide Clinical Trials Controlled Quality Management Document			
 WORLDWIDE CLINICAL TRIALS	Sponsor:	TB Alliance	
	Protocol Number:	TBI-223-CL-001	
STATISTICAL ANALYSIS PLAN – PHASE 1			

Listing Number	Listing Title	Validation Method	Shell Number (if repeat)
16.2.6.11	Statistical Analysis SAS Output (SR Fed vs IR Fed; Part 2)	MR	
16.2.7	Adverse Event Listings		
16.2.7.1	Adverse Event Data – Safety Analysis Set	IP	
16.2.8	Individual Laboratory Measurement and Other Safety		
16.2.8.1	Hematology Data – Safety Analysis Set	IP	
16.2.8.2	Serum Chemistry Data – Safety Analysis Set	IP	

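### SAP 6.11 analyses IR tablet fed vs fasted as parallel groups although the same six subjects take both doses; with positive within-subject correlation its 90% CI is too wide

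*SAP*

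**What the plan says.** **The model.** Under its Part 2 heading, SAP 6.11 compares Cmax, AUClast and AUCinf with an "Analysis of Variance (ANOVA) model for a parallel design on the ln-transformed data with treatment as a fixed effect". Conclusions rest on the geometric mean ratio and its 90% confidence interval. The first comparison listed is IR 2000 mg "FED (Cohort 9) vs. IR, 2000 mg (2 x 1000 mg tablets) / FASTED (Cohort 8").

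**The subjects.** SAP Section 1 states: "The 6 subjects from Arm 4, who received the IR tablet formulation will be brought back following a 7-day washout period". Protocol Section 3, Part 2, agrees: "The 6 subjects from Cohort 8, Arm 4, who received the IR tablet formulation fasted will return after a 7-day washout". So does Protocol 6.4: "Please note that Cohort 9 is the same 6 subjects that were in Cohort 8, Arm 4 (IR tablet formulation) under fed conditions". New volunteers come in only if more than two of the six drop out, and at least four subjects are needed to complete the fed cohort.

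**The other same-subject comparisons.** Also in SAP 6.11, Cohort 5 fed/fasted is modelled "with treatment as the fixed effects and subject as a random effect", and the Cohort 3 repeat (capsule against suspension) "with treatment as a fixed effect and subject as a random effect".

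**The outputs.** The comparison has its own table (14.4.16) and its own listing (16.2.6.9): "Statistical Analysis SAS Output for Food Effect Assessment (IR tablets; Part 2").

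Protocol 9.2 and 9.3 ask only for an ANOVA approach. SAP Section 7 records no change to the planned analyses, and nothing explains why Part 2 drops the subject effect.

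**The concern.** A parallel-design ANOVA treats the 12 IR observations as coming from 12 independent people. If six people supply both values, the fed-minus-fasted difference is a within-subject contrast, and only within-subject variance should enter its error. The planned model also leaves between-subject variance there, so the standard error is overstated whenever a subject's two values are positively correlated.

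The SR prototypes are given only fed, so IR fed against IR fasted is the one comparison that isolates food for a tablet. It serves the secondary objective on rate and extent of absorption (SAP 2.2). Bringing the Arm 4 subjects back buys precision at n=6, and the planned model gives that precision away.

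**Working it through.** There is no planned figure to reproduce: the study is not formally powered, and neither document gives a CV or a within-subject correlation.

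**Inputs from the documents.** Six subjects, each dosed fasted then fed; ln-transformed data; 90% two-sided interval.

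**Assumed inputs.** Between-subject CV (CVb) 20–40%, within-subject CV (CVw) 10–30%, six complete pairs. SD on the ln scale: s = √ln(1+CV²).

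**Formulas.** Let ρ = sB²/(sB²+sW²).

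- Parallel half-width: t(0.95, df) × √[2(sB²+sW²)/6]. Here df = 10 and t = 1.812 if only the two IR conditions are fitted. If all five Part 2 treatments share one ANOVA, df = 30 − 5 = 25 and t = 1.708.
- Paired half-width: t(0.95, 5) × √[2sW²/6], with t = 2.015.
- The parallel SE exceeds the true SE by the factor 1/√(1−ρ).

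**Worked case, CVb 30%, CVw 15%.**

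- sB² = ln(1.09) = 0.0862; sW² = ln(1.0225) = 0.0223; ρ = 0.0862/0.1084 = 0.79.
- Parallel: 1.812 × √(2 × 0.1084/6) = 1.812 × 0.190 = 0.345.
- Paired: 2.015 × √(2 × 0.0223/6) = 2.015 × 0.086 = 0.174.

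These insert the true SDs. Sample half-widths have slightly lower medians, 0.324 and 0.162. Around a ratio of 100%, those medians give 72–138% (parallel) and 85–118% (paired).

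**Simulation over the assumed range** (200,000 trials for each of 25 CV pairs, two-condition fit):

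| CVb / CVw | ρ | Coverage of parallel 90% CI | Median half-width, parallel / paired | Ratio |
|---|---|---|---|---|
| 20% / 30% | 0.31 | 94.5% | 0.356 / 0.319 | 1.12 |
| 30% / 15% | 0.79 | 99.5% | 0.324 / 0.162 | 2.00 |
| 40% / 10% | 0.94 | over 99.9% | 0.389 / 0.108 | 3.59 |

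Paired coverage was 89.9–90.3% throughout. The closed-form SE factor runs from 1.2 (ρ = 0.31) to 4.0 (ρ = 0.94), in line with these results.

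**By correlation alone**, including values below that range (coverage simulated; width ratio parallel/paired from the formulas):

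| ρ | Coverage, two-condition fit | Coverage, five-treatment fit | Width ratio, df 10 | Width ratio, df 25 |
|---|---|---|---|---|
| 0 | 90.0% | 89.8% | 0.90 | 0.85 |
| 0.2 | 92.9% | 93.3% | 1.01 | 0.95 |
| 0.5 | 96.8% | 97.6% | 1.27 | 1.20 |
| 0.7 | 98.8% | 99.5% | 1.64 | 1.55 |
| 0.8 | 99.5% | 99.9% | 2.01 | 1.90 |
| 0.9 | 99.9% | about 100% | 2.84 | 2.68 |

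**Break-even.** The parallel interval is the wider one once 1−ρ < [t(df)/t(5)]². For df 10 this is ρ > 1 − (1.8125/2.0150)² = 0.19; for df 25 it is ρ > 0.28.

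**Incomplete pairing** (ρ 0.5 and 0.8). With three of six replaced by new volunteers, parallel coverage is 93.7% and 96.1%. With four returners and no replacement it is 95.5% and 98.6%.

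**Illustration of the lost precision.** The chance that the 90% CI lies above 100% when the true ratio is 1.30 is 30% parallel against 83% paired at CVb 30%/CVw 15%. At 20%/30% it is 30% against 38%. Over the whole grid it is 14–69% against 38–99%. The SAP sets no such decision rule for Part 2.

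**The case against.** **The size rests on assumed CVs.** This stands. The grid covers only ρ from 0.31 to 0.94. At CVb 15%/CVw 30%, coverage is 92.9% and the width ratio 1.04; at 10%/30% they are 91.6% and 0.99. With 5 df against 10, pairing gains little or nothing when correlation is low. The stated level is still wrong for any ρ above zero.

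**The data may be only partly paired.** This is possible: Cohort 9 may finish with four subjects or with replacements. The parallel interval still over-covers in the cases computed above, and a mixed model uses paired and unpaired subjects alike.

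**A subject term does not remove period effects.** True. Everyone is dosed fasted first and fed second, so food and period are confounded under either model. Cohort 5 has the same fixed order, and there the SAP does include subject.

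**One five-treatment fit would carry the repeated IR values into the SR comparisons.** The SAP does not say whether each comparison is fitted separately. The SR vs IR contrasts still involve different people, so a parallel model suits them. For the IR contrast, the five-treatment fit changes the figures little.

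**The consequence is limited, and the study report may add analyses (SAP Section 6).** Both are true, but an option to add an analysis later does not correct the prespecified one.

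**Conclusion.** The concern holds. For IR fed against IR fasted, the planned model does not match the planned design, and it departs from the SAP's own treatment of its two other same-subject comparisons. Under the assumed CVs, the nominal 90% interval is in truth a 94.5% to over 99.9% interval, with a median half-width 1.1 to 3.6 times the paired one. At low correlation the effect shrinks towards nothing.

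The error is conservative: it does not create false food-effect claims. Part 2 has no equivalence criterion to fail. The SR vs IR comparisons are not in question. This should be fixed because the interval is the reported result, its stated level is wrong, and the correction is cheap.

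**What to change.** In SAP 6.11, Part 2, change the first comparison only: ln-transformed Cmax, AUClast and AUCinf, treatment fixed, subject random, fitted as a mixed model so that any unpaired replacements still contribute. Link each subject's Cohort 8 Arm 4 and Cohort 9 records. Keep the parallel ANOVA for the SR vs IR comparisons.

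In the same edit, name the degrees-of-freedom method and note that the fixed fasted-then-fed order confounds food with period. Also reconcile the minimum of four subjects for Cohort 9 (Protocol Section 3 and 6.1; SAP Sections 1 and 4) with the minimum of six per Part 2 arm in Protocol Appendix 6, since this sets the number of pairs.

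The model change costs one sentence in the SAP and a few lines of code for Table 14.4.16 and Listing 16.2.6.9. No new data are needed.

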6.12 Safety Analyses

The safety analyses will be presented by the treatment received for the Safety Analysis Set.

QMD Ref: Worldwide-TMP-ST-006-4.0 Effective: 12Aug2019	Governing QMD: Worldwide-SOP-ST-001
Confidentiality Statement	

This document is the property of Worldwide Clinical Trials Inc. and may not be duplicated, copied, altered or removed from company without prior approval from Worldwide Quality Assurance or in compliance with Worldwide Standard Operating Procedures.

Worldwide Clinical Trials Controlled Quality Management Document			
 WORLDWIDE CLINICAL TRIALS	Sponsor:	TB Alliance	
	Protocol Number:	TBI-223-CL-001	
STATISTICAL ANALYSIS PLAN – PHASE 1			

